6.3. Other Endpoints

- Viral load
- Body temperature: If more than one measurement is taken on the same day regardless of before or after the start of treatment with this drug, the higher value will be used for the analysis.
- Percutaneous arterial oxygen saturation (SpO₂): If more than one measurement is taken on the same day regardless of before or after the start of treatment with this drug, the lower value will be used for the analysis.

6.4. Covariates

In Study C4671005, subgroup analyses of COVID-19-related hospitalization or death (all causes) reported up to Day 28, an efficacy endpoint, were performed for age, sex, race, BMI, serology, viral load, comorbidities, and number of comorbidities. The results were consistent with those in the whole mITT population in many subgroups and the incidence was significantly or more decreased in the subgroups with a large number of subjects or with a high incidence (Study C4671005, Interim Clinical Study Report). These will not be used as covariates in this study.

While the impact of viral variants and SARS-CoV-2 vaccination history on efficacy has not been evaluated in clinical studies, they are potential covariates.

Since HIV-infected patients may concomitantly use anti-HIV therapy including ritonavir with this drug, this is a potential covariate for the safety of this drug.

7. HANDLING OF MISSING DATA

If the seriousness, causal relationship, treatment, and outcome of an adverse event are missing, the data will be handled as "unknown" for tabulation.

If there are no measured values within the acceptable window for each time point of evaluation of efficacy endpoints (Appendix 2), the values will be handled as missing and will not be imputed. Definitions of acceptable windows for other endpoints are provided in Appendix 2.

If the date of admission is missing or partial, the last complete date among the following will be used as the imputed date.

- Start date of this drug
- The first day of the month of the same month as the date of admission (if the day of admission is missing and the month and year are available)
- The first day of the year of the same year as the date of admission (if the month and day of admission are missing and the year is available)

If the date of death and the date of last observation are missing or partial, the latest complete date among the following will be used as the imputed date.

- Start date/end date of this drug
- Start date/end date of concomitant drug therapy
- Start date/end date of concomitant non-drug therapy
- Viral test
- Date of measurement of body temperature/SpO₂
- Date of admission/date of discharge
- Date of efficacy evaluation (date of the highest severity/date of evaluation at the end of the observation period)
- Date of onset of adverse event, resolution/recovery of adverse event, date of death
- The first day of the month of the same month as the date of last observation (if the day of last observation is missing and the month and year are available)
- The first day of the year of the same year as the date of last observation (if the month and day of last observation are missing and the year is available)

The policy for handling uncleaned data is described below.

- Items of missing data: Values will be handled as missing (category of categorical variables is "not recorded") in both tabulation and listing.
- Items of inconsistent data: Inconsistent data will be handled as missing in both tabulation and listing. However, a list of data handling will be prepared separately.
- No signature: The descriptions in the CRF without the signature of the contract physician (including the case of only the signature of a physician other than the contract physician) will be handled as missing in both tabulation and listing.

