#### 8.3.10. Adverse events

Occurrence of adverse events from the start date of administration of this drug to the end date of the observation period should be confirmed and the following information should be recorded.

Also, further investigation should be separately conducted, if deemed necessary by Sponsor for patients who experienced a serious adverse reaction, an unexpected adverse reaction or other adverse reactions not listed in the package insert.

- Presence/absence of adverse event
- Name of adverse event
- Date of occurrence
- Intervention
- Seriousness
- Outcome
- Causal relationship to this drug

If the adverse event is associated with abnormal laboratory values, i.e., clinical laboratory tests, the following information should also be recorded.

- Date of tests
- Name of laboratory test
- Site reference value
- Site unit
- Test results

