# 8.6. Data management

# 8.6.1. Case report forms (CRFs)/ Electronic data record

As used in this full protocol, the term CRF should be understood to refer to an electronic data record, depending on the data collection method used in this study.

A CRF is required and should be completed for each included patient. The completed original CRFs are the sole property of Pfizer and should not be made available in any form to third parties, except for authorized representatives of Pfizer or appropriate regulatory authorities, without written permission from Pfizer. The investigator shall ensure that the CRFs are securely stored at the study site in encrypted electronic form and will be password protected or secured in a locked room to prevent access by unauthorized third parties.

The investigator has ultimate responsibility for the collection and reporting of all clinical, safety, and laboratory data entered on the CRFs and any other data collection forms (source documents) and ensuring that they are accurate, authentic/original, attributable, complete, consistent, legible, timely (contemporaneous), enduring, and available when required. The CRFs must be signed by the investigator or by an authorized staff member to attest that the data contained on the CRFs are true. Any corrections to entries made in the CRFs or source documents must be dated, initialed (or stamped "correction seal"), and explained (if necessary) and should not obscure the original entry.

The source documents are the hospital or the physician's chart. In these cases, data collected on the CRFs must match those charts.

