#### **8.6.5.3.** Submission

After data entry and revision are completed, CRFs should be signed electrically by the investigator following confirmation of entry and follow-up survey.

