5. ANALYSIS SETS

5.1. Safety Analysis Set

The safety analysis set is defined as the full analysis set that is as close as possible to all patients treated with this drug. Specifically, the safety analysis set is defined as a population of registered or reported patients excluding those who meet any of the following conditions:

- 1. The CRF could not be collected at all (description in the report, "CRF not collected")
- 2. There was a violation or flaw in the contract (description in the report, "contract violation/flaw")
- 3. There was a violation of registration (description in the report, "violation of registration")
- 4. Administration of the study drug has not been reported at all (description in the report, "no information on administration")

5. Information on adverse events has not been reported at all - no visits after the first prescription day (description in the report, "no information on adverse events - no re-visits")

6. Information on adverse events has not been reported at all - there is a visit after the first prescription day but no description of information (description in the report, "no information on adverse events - no description")

The details of each criterion are based on the latest guidance.

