8.2.3. Safety analysis

Refer to Section 6.1 for the evaluation period for adverse reactions and adverse events. The listing will include all events reported in this study.

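### CRF entries lacking the contract physician's signature at analysis are dropped from tables and listings, with no exception for adverse events or deaths and no record of what was dropped

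*SAP*

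**What the plan says.** SAP section 7 ends with rules for data not resolved by the time of analysis, introduced by "The policy for handling uncleaned data is described below". The last rule concerns signatures. It covers "The descriptions in the CRF without the signature of the contract physician", and its scope continues: "including the case of only the signature of a physician other than the contract physician) will be handled as missing in both tabulation and listing".

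Three other places bear on it:

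- Protocol 8.6.1, on who may attest a CRF: "The CRFs must be signed by the investigator or by an authorized staff member".
- Protocol 8.6.5.3, on submission through the EDC system: "CRFs should be signed electrically by the investigator following confirmation of entry and follow-up survey".
- SAP 8.2.3, on safety output: "The listing will include all events reported in this study".

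Adverse events are CRF items. Protocol 8.3.10 states: "Occurrence of adverse events from the start date of administration of this drug to the end date of the observation period should be confirmed", with the details to be recorded. The table in protocol 10.1 has all serious and all non-serious adverse events entered on the CRF.

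**The concern.** The signature rule is an attestation rule, but it acts on content. An adverse event that a site has entered in the EDC system, and that the sponsor can see, is treated as if it had never been entered. The wording covers CRF descriptions in general, so it reaches adverse events, outcomes and deaths as well as background items.

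Part of the aim of this study, in the sample size rationale, is to see at least one case of a previously unknown reaction. For that aim a single reported event matters, and it should not be possible to lose one without trace. The inconsistent-data rule just above also blanks data, but promises a separate list of how they were handled. The signature rule has no such provision, so a reader of the report could not tell that anything had been removed.

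**Working it through.** **1. The plan's own figures.** Inputs from protocol 8.5: target 3000 in the safety analysis set, 7.8% with adverse reactions, a rare reaction at 0.1%.

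- Rare reaction: n = ln(0.05)/ln(1 − 0.001), rounded up, is 2995. At n = 3000, 1 − 0.999^3000 = 95.03%. The stated 95% reproduces.
- Common reactions: for X ~ Bin(3000, 0.078), P(X ≥ 214) = 92.0%. The largest count reached with at least 90% probability is 215 (90.9%). The stated 214 is slightly conservative.

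Neither figure is in dispute.

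**2. Who may sign.**

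- Protocol 8.6.1: the investigator or an authorized staff member.
- Protocol 8.6.5.3: the investigator.
- SAP 7: the contract physician only; another physician's signature alone does not count.

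The SAP does not define the contract physician against either protocol term. A CRF with no signature at all fails all three passages. The conflict with 8.6.1 is confined to CRFs signed by someone whom 8.6.1 would accept but who is not the contract physician.

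**3. Tracing a reported reaction on such a CRF.**

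- *Tables and listings:* removed from both under SAP 7.
- *Safety set:* condition 6 of SAP 5.1 excludes patients whose adverse event information was never reported, where "there is a visit after the first prescription day but no description of information". Blanked entries might be treated this way. The SAP does not say so, and it refers the details to guidance that is not among the documents.
- *Output for excluded patients:* SAP 8.2.3.1.6 lists and tabulates reactions in CRF-collected patients outside the safety set, and SAP 9 plans related listings. Section 7 applies to listings without exception, so on its wording these would not recover the event.
- *Deaths:* SAP 6.2 confirms death from adverse event outcome data. Without the adverse event page, Table 1 in SAP Appendix 1 classes death as unknown (cases 2, 5 and 6). With all three pages empty, the patient also leaves Efficacy Analysis Set 1 (case 8).
- *Second route:* protocol 10.1 sends serious events and listed exposure scenarios (with any associated event) to the sponsor within 24 hours. Protocol 10.3 adds events of unknown causality. Other non-serious events have no such route. The documents do not say whether reports received this way enter the study tables.

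**4. Size.** The unsigned share, u, is not in the documents. Purely as an illustration on 3000 patients at 7.8% (234 expected with reactions), the expected number of patients whose reactions go unseen is 234 × u:

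- u = 1%: 2.3
- u = 5%: 11.7
- u = 10%: 23.4

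If these patients stay in the denominator with their events blanked, the expected proportion is 7.8% × (1 − u): 7.72%, 7.41% and 7.02%. If they leave numerator and denominator together, it stays at 7.8% unless missing signatures are related to reactions.

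**The case against.** Four arguments carry weight.

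- *It is a residual rule.* Queries, correction and the investigator's signature come first (protocol 8.6.5.2 and 8.6.5.3), and nothing shows that any CRF will remain unsigned. This stands and limits the likely size, but it does not justify leaving no trace.
- *SAP 7 is close to protocol 8.6.5.3.* A reader might infer that the SAP overrides a settled protocol rule. The documents do not support that: the protocol gives two rules, and the SAP is near one of them. What stands is that three passages need aligning.
- *The listing sentence in SAP 8.2.3 may be about time only.* It follows a reference to the evaluation period, so it may mean just that listings are not cut off at the end of that period. This is a fair reading. The sentence nevertheless speaks of all reported events without qualification, and section 7 does not say which prevails.
- *There may be a sound reason to keep unattested data out of regulatory tables.* Accepted. That is a reason for a rule on the main tables, not for removing events from listings as well.

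A reader might also infer that detection of a 0.1% reaction falls below 95%, for example by subtracting 5% from 3000. The documents do not support that: 3000 is the target for the safety set after exclusions, and the number to be registered beyond it is not given. Nor do they support saying that affected patients are certainly excluded from the safety set, or that serious events and deaths never reach the sponsor; the first is not stated, and the 24-hour route covers the second.

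**Conclusion.** The concern holds as a reporting gap. On its wording, SAP section 7 removes reported adverse events and deaths from tables and listings when the contract physician's signature is outstanding, and leaves no record. That is at odds with the literal text of SAP 8.2.3 and with protocol 8.6.1, while protocol 8.6.5.3 points another way.

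The conclusion assumes that CRF descriptions include adverse event entries. The rule does not name them, but its wording is unrestricted and both documents treat adverse events as CRF content. The number of patients affected cannot be derived and may be small or nil. No shortfall in sample size or detection probability is claimed. The point merits correction because the study looks for single unknown reactions, and because the remedy is cheap.

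**What to change.** 1. Reconcile the signature wording in protocol 8.6.1, protocol 8.6.5.3 and SAP 7, and define the contract physician in relation to the investigator and authorized staff.
2. In SAP 7, keep the contract-physician rule for the main tables if it is needed there, but state that adverse events and deaths on CRFs without that signature always appear in the listings, flagged *signature outstanding*.
3. Report the number of affected patients, and give the adverse reaction count with and without them.
4. State in SAP 5.1 whether such patients count as having no adverse event information.

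The cost is SAP wording, a matching clarification in the protocol, one flag and one sensitivity count; no new data are collected. The small downside is that some unattested data are shown, but they are labelled as such.

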8. STATISTICAL METHODS AND ANALYSES

8.1. Statistical Methods

8.1.1. Continuous variables

For continuous variables, summary statistics (n, mean, standard deviation, median, 1st quartile, 3rd quartile, maximum, and minimum) will be calculated.

8.1.2. Categorical variables

For categorical variables, patients falling into each category will be summarized in terms of frequency and proportion.

8.1.3. Binary variables

For binary variables, patients falling into each binary category will be summarized in terms of frequency and proportion. When a confidence interval is calculated for a proportion, the two-sided 95% confidence interval (exact method) will be calculated.

When a comparison for proportion is made between subgroups, the risk ratio and its 95% confidence interval will be calculated. In addition, the risk ratio and its 95% confidence interval will be graphically presented.

If a test is performed, Fisher's exact test will be used for the relationship with nominal scale data and Cochran-Armitage test (exact method) for the relationship with ordinal scale data. However, if it is difficult to perform the exact method, a chi-square test or Cochran-Armitage test with normal approximation will be used as an alternative to the exact method.

8.1.4. Time (to event) data

Kaplan-Meier's method will be used to determine the median, 1st quartile, and 3rd quartile. The time point incidence will be calculated on Days 3, 5, 7, 14, 21, and 28 after the start of treatment with this drug (the start date of treatment will be defined as Day 1). Confidence intervals will be estimated using the log-log transformation (corresponding to specifying a loglog under the conftype option in the proc lifetest statement of the SAS®, lifetest procedure). In addition, Kaplan-Meier plots will be prepared.

When time data are compared between subgroups, the hazard ratio of events and its 95% confidence interval will be calculated using Cox proportional hazard model (Breslow method for handling ties). In addition, the hazard ratio and 95% confidence interval will be graphically presented.

8.2. Statistical Analyses

Analyses in the safety analysis set and the efficacy analysis set will also be performed in the consented safety analysis set and the consented efficacy analysis set, but the details will be separately specified. At the time of analysis, the safety analysis set and the efficacy analysis set will be replaced with the consented safety analysis set and the consented efficacy analysis set, respectively.

8.2.1. Description of patients

8.2.1.1. Constitution

The numbers of patients who completed the study, patients included in safety analysis, patients included in efficacy analysis 1, patients included in efficacy analysis 2, and patients included in efficacy analysis 3 will be determined. In addition, CRF-uncollected patients, patients excluded from safety analysis, patients excluded from efficacy analysis 1, patients excluded from efficacy analysis 2, and patients excluded from efficacy analysis 3 will be counted as a total and by reason for exclusion.

8.2.1.2. Discontinuation

In the safety analysis set, Efficacy Analysis Set 1, Efficacy Analysis Set 2, and Efficacy Analysis Set 3, the number and proportion of patients who discontinued the study will be summarized by timing (during treatment, within 7 days after the end of treatment, within 14 days after the end of treatment, within 21 days after the end of treatment, and within 28 days after the end of treatment). The same summarization will also be performed by reason of discontinuation. The number and proportion of completed patients will be summarized.

8.2.1.3. Patients excluded from analysis

Patients excluded from safety analysis, patients excluded from efficacy analysis 1, patients excluded from efficacy analysis 2, and patients excluded from efficacy analysis 3 will be listed in tabular form with their reason for exclusion.

8.2.2. Patient characteristics and treatment history

8.2.2.1. Patient characteristics

In the safety analysis set, Efficacy Analysis Set 1, Efficacy Analysis Set 2, and Efficacy Analysis Set 3, the following patient characteristics will be summarized in accordance with Section 8.1:

- Sex [male, female]
- Age (continuous)
- Age [<15 years, \ge 15 years]
- Age [<65 years, ≥65 years]
- Age [<18 years, \ge 18 years]
- Age [<65 years, ≥65 to <75 years, ≥75 years]
- Age $[\ge 60 \text{ years}] * \ge 60 \text{ years}$ is a risk factor for aggravation.
- Age and body weight [\geq 12 to <18 years and \geq 40 kg, \geq 6 to <12 years and \geq 40 kg, \geq 6 to <18 years and \geq 20 to <40 kg, \geq 6 to <18 years and <20 kg, \geq 2 to <6 years, <2 years]

- Pregnancy [absent, present] * Female only
- Inpatient/outpatient status at the start of treatment with this drug [outpatient, inpatient]
- Reason for hospitalization at the start of treatment with this drug [treatment of infection caused by SARS-CoV-2, isolation, other]
- BMI [\leq 25 kg/m², >25 kg/m², unknown] * \geq 25 kg/m² is a risk factor for aggravation.
- Smoking status [no, smoked in the past, smoking, unknown] * "Smoking" is a risk factor for aggravation.
- Disease subject to the study [infection caused by SARS-CoV-2, other]
- Symptoms of infection caused by SARS-CoV-2 [present, absent, unknown]
- Number of days from the onset of symptoms of infection caused by SARS-CoV-2 to the start of treatment with this drug [within 3 days, 4 or 5 days, 6 days or more, unknown] (If the onset of symptoms and the start of treatment with this drug are observed on the same day, the number of days will be 0.)
- Severity of symptoms of infection caused by SARS-CoV-2 [mild, moderate I, moderate II, severe, unknown]
- Hepatic impairment [absent, present, unknown] [if present: mild, moderate, severe, unknown]
- Renal impairment [absent, present, unknown] [if present: mild, moderate, severe, unknown]
- Medical history [absent, present]
- History of infection caused by SARS-CoV-2 [absent, present]
- Complications [absent, present]
- Complications corresponding to risk factors for aggravation of infection caused by SARS-CoV-2
 [absent, present] * "Present" is a risk factor for aggravation.
- Risk factors for aggravation of infection caused by SARS-CoV-2 [absent, present, unknown] [if present: 1, 2, 3, 4, number unknown] * If the number of applicable risk factors is unknown, "number unknown" should be selected. If it is not known that there are risk factors, the patient will be classified as "unknown."
- Complicated with HIV infection and concomitantly using anti-HIV therapy including ritonavir or cobicistat [absent, present] * Specifically, patients concomitantly using ritonavir or cobicistat will be classified as present and other patients as absent.
- Prior medications for infection caused by SARS-CoV-2 [absent, present, unknown]

- Breakdown of prior medications for infection caused by SARS-CoV-2 [remdesivir (Veklury),
 molnupiravir (Lagevrio), dexamethasone, baricitinib (Olumiant), casirivimab/imdevimab
 (Ronapreve), sotrovimab (Xevudy), tocilizumab (Actemra), tixagevimab/cilgavimab (Evusheld),
 ensitrelvir fumarate (Xocova), other] * Categories will be set appropriately for drugs for the treatment
 of infection caused by SARS-CoV-2 in addition to the drugs listed.
- Prior medications for infection caused by SARS-CoV-2 (continued at the start of treatment with this drug) [absent, present, unknown]
- Breakdown of prior medications for infection caused by SARS-CoV-2 (continued at the start of treatment with this drug) [remdesivir (Veklury), molnupiravir (Lagevrio), dexamethasone, baricitinib (Olumiant), casirivimab/imdevimab (Ronapreve), sotrovimab (Xevudy), tocilizumab (Actemra), tixagevimab/cilgavimab (Evusheld), ensitrelvir fumarate (Xocova), other] * Categories will be set appropriately for drugs for the treatment of infection caused by SARS-CoV-2 in addition to the drugs listed.
- SARS-CoV-2 vaccination history (vaccination on or before the day before the start of treatment with this drug) [absent, present, unknown]
- Breakdown of SARS-CoV-2 vaccination history (vaccination on or before the day before the start of treatment with this drug) [Comirnaty, Spikevax, Vaxzevria, other, unknown]
- Number of SARS-CoV-2 vaccination doses (vaccination on or before the day before the start of treatment with this drug) [absent, present, unknown] [if present: 1, 2, 3, 4 or more]
- SARS-CoV-2 viral test before the start of treatment with this drug (including the start date of treatment) [present, absent]
- Results of SARS-CoV-2 viral test before the start of treatment with this drug (including the start date of treatment) [positive, negative]
- SARS-CoV-2 viral load (continuous) before the start of treatment with this drug (including the start date of treatment)
- SARS-CoV-2 viral load before the start of treatment with this drug (including the start date of treatment) [≥4 log₁₀ copies/mL, <4 log₁₀ copies/mL, unknown] [≥7 log₁₀ copies/mL, <7 log₁₀ copies/mL, unknown]
- SARS-CoV-2 variant before the start of treatment with this drug (including the start date of treatment) (wild strain, Beta variant, Gamma variant, Delta variant, Omicron variant, unknown)
- Percutaneous arterial oxygen saturation (SpO₂) before the start of treatment with this drug (including the start date of treatment) [\geq 96%, \geq 93% to \leq 96%, \leq 93%, unknown]
- Percutaneous arterial oxygen saturation (SpO₂) before the start of treatment with this drug (including the start date of treatment) [≥95%, <95%, unknown]

• Findings of pneumonia due to infection caused by SARS-CoV-2 at the start of treatment with this drug [absent, present, unknown]

- Administration of oxygen for infection caused by SARS-CoV-2 performed since before the start of treatment with this drug [present]
- Artificial ventilation with intubation for infection caused by SARS-CoV-2 performed since before the start of treatment with this drug [present]
- ECMO for infection caused by SARS-CoV-2 performed since before the start of treatment with this drug [present]

Using the safety analysis set, the following aspects of patients will be summarized in terms of number and proportion by system organ class (SOC) and by preferred term (PT):

- Breakdown of medical history
- Breakdown of complications
- Breakdown of complications (those corresponding to risk factors for aggravation of infection caused by SARS-CoV-2)

In the safety analysis set, Efficacy Analysis Set 1, Efficacy Analysis Set 2, and Efficacy Analysis Set 3, the following number and proportion of patients will be tabulated. All the therapies used between the start date of treatment with this drug and Day 28 after the end of treatment will be included.

- Breakdown of concomitant drug therapies (those other than SARS-CoV-2 vaccines whose reason for use is infection caused by SARS-CoV-2) [remdesivir (Veklury), molnupiravir (Lagevrio), dexamethasone, baricitinib (Olumiant), casirivimab/imdevimab (Ronapreve), sotrovimab (Xevudy), tocilizumab (Actemra), tixagevimab/cilgavimab (Evusheld), ensitrelvir fumarate (Xocova), other]
 * Categories will be set appropriately for drugs for the treatment of infection caused by SARS-CoV-2 in addition to the drugs listed.
- Breakdown of other concomitant drug therapies (those other than SARS-CoV-2 vaccines whose reason for use is infection caused by SARS-CoV-2)
- Breakdown of concomitant drug therapies (those other than SARS-CoV-2 vaccines whose reason for use is other than infection caused by SARS-CoV-2)
- Breakdown of concomitant drug therapies (SARS-CoV-2 vaccines)
- Breakdown of concomitant non-drug therapies (those whose reason for use is infection caused by SARS-CoV-2)
- Breakdown of concomitant non-drug therapies (those whose reason for use is adverse events)

